8.1 General Considerations

All data will be presented in listings, and summary tables and/or graphs will be provided, as appropriate. Unless otherwise noted, all tabulations for efficacy endpoints will be presented for subjects in the Primary Efficacy Analysis Set and tabulations for other endpoints will be presented for subjects in the Full Analysis Set (FAS). Descriptive summary statistics (n, mean, median, standard deviation, minimum and maximum) will be calculated for the continuous variables. Shift tables and/or frequencies and percentages will be produced for the categorical variables. When percentages are reported, the number of treated subjects will be used as the denominator. As noted, 95% two-sided confidence intervals (CIs) will be calculated around the estimates based on the exact binomial distribution for binomial endpoints and the t-distribution for continuous endpoints.

Baseline will be defined as the last measurement prior to the first infusion of sebelipase alfa. (Note: For exploratory analyses, the first available measurement after initiation of treatment may be used as baseline if a pretreatment measurement is unavailable.) Survival rates will be based on the age of the subject. Other endpoints, unless otherwise noted, will be based on exposure (i.e., duration of time since the first infusion of sebelipase alfa).

Details of the planned analyses and statistical methodologies will be provided in a separate Statistical Analysis Plan (SAP).

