8.7 Efficacy Analysis

Efficacy will be analyzed for the Primary Efficacy Analysis Set. If the PPS is not identical to the Primary Efficacy Analysis Set (i.e., if at least one patient in the Primary Efficacy Analysis Set is excluded from the PPS), efficacy analyses will be repeated for the PPS.

The primary efficacy endpoint is the proportion of subjects surviving to 12 months of age. It is not anticipated that any subjects will be lost to follow-up prior to 12 months of age, but a subject who is not confirmed to have survived to 12 months of age will not be considered to have met the primary endpoint. As a complementary analysis, Kaplan-Meier survival curves of survival since birth and survival since first dose of IMP will be presented.

Survival at 18 and 24 months of age will be analyzed as described for the primary endpoint. Median age at death will also be calculated. A Kaplan-Meier estimate of median survival past first dose of IMP will be computed.

Estimated survival rates and median age at death derived from this study will be compared to rates/times reported in the literature, and will be discussed in conjunction with information derived from a natural history study in a similar patient population (study LAL-1-NH01).

Anthropometric indicators of growth, standardized by age and gender in accordance with the methodology described by the WHO and using WHO growth charts will be listed by study time point as observed values and as changes from baseline. Change from baseline in anthropometric data will be tabulated as continuous data. In addition, the percentages of subjects who meet criteria for underweight, stunting, and wasting will be tabulated for each timepoint. For anthropometric indicators of growth, age will be adjusted for prematurity if gestational age is <37 weeks and the subject is under 12 months of age. The adjustment will be made such that corrected age = chronological age minus the number of months premature.

Change and/or percent changes from baseline in AST, ALT, and serum ferritin will be tabulated for each evaluation timepoint.

A subject will be considered to have achieved transfusion-free hemoglobin normalization (TFHN) if the subject meets all of the following criteria:

- 1. Has two post-baseline measurements of hemoglobin at least 4 weeks apart that are both above the age-adjusted lower limit of normal (LLN);

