7. GENERAL ISSUES FOR STATISTICAL ANALYSIS

7.1 General Statistical Methodology

All data will be presented in patient data listings. Descriptive summaries and/or graphics will be provided where appropriate for each of the analysis variables.

Continuous quantitative variable summaries will include the number of subjects (n) with non-missing values, mean, standard deviation, minimum, first quartile (Q1), median, third quartile (Q3), and maximum.

Shift tables and/or frequencies and percentages will be produced for categorical variables. In general, the denominator for the percentage calculation will be based upon the total number of subjects in the study population for the group, unless otherwise specified.

Listings with the potential for multiple timepoints per topic (eg, labs) will have Dosing Regimen at Time of Xxxx. Dosing Regimen at Time of the assessment/event/etc will be the dose that preceded the assessment (ie, not necessarily the dose given on the day of the assessment). Vital Signs and AEs/IRRs occurring during or following an infusion should have the dose associated with the infusion – ie, the dose administered during the infusion.

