7.1.1 Handling of Missing Data

All data will be analyzed as they were collected in the database. Missing data will not be imputed.

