9.1 Efficacy Endpoint Analysis

The primary endpoint is the proportion of subjects surviving to 12 months of age. A 95% exact confidence interval, calculated using the Clopper-Pearson method [Clopper and Pearson, 1934], will also be presented.

It is not anticipated that subjects will be lost to follow-up prior to 12 months of age; however, subjects in the PES who are not confirmed to have survived to 12 months of age will not be considered to have met the primary endpoint. As a complementary analysis, Kaplan-Meier survival curves of survival since birth and survival since first dose of SBC-102 will be presented. A Kaplan-Meier estimate, with 95% CI if appropriate, of median survival post first dose of SBC-102 will also be provided.

The proportion of subjects surviving to 18 and 24 months of age will also be analyzed as described for the primary endpoint (i.e., percent of subjects in the PES surviving to 18 and 24 months). These proportions will also be estimated by Kaplan-Meier (product-

limit) methodology if there are subjects whose survival times are censored prior to 18 or 24 months.

The median age at death will be calculated and presented in a summary table. The median will also be estimated by Kaplan-Meier (product-limit) methodology.

Estimated survival rates and median age at death derived from these analyses will be compared to rates/times reported in the literature, and will be discussed in conjunction with information derived from the natural history study in a similar patient population (study LAL-1-NH01). Further, a separate Kaplan-Meier survival curve for survival from birth will be constructed for the patient population in LAL-1-NH01.

Anthropometric indicators of growth, standardized by age and gender in accordance with the methodology described by the WHO and using WHO growth charts will be listed by study time point as observed values and as changes from baseline. Change from baseline in anthropometric data will be tabulated as continuous data. In addition, the percentages of subjects who meet criteria for underweight (<-2 standard deviations [SD] from the median for WFA), stunting (<-2 SD from the median for LFA/HFA), and wasting(<-2 SD from the median for WFL/WFH) will be tabulated for each timepoint.

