12.1 Analysis Set Summary Conventions

- Analysis sets represented on the tables will be clearly identified at the end of the table title and will be identical in name to that identified in the protocol or SAP: (Full Analysis Set), (Primary Efficacy Analysis Set), and (Per-Protocol Analysis Set).
- In general, all data recorded will be included in data listings. For listings that include screen failure data, the screen failure subject IDs will be sorted at the end of each listing.
- Consistent terminology will be used to define and identify a population. Common nomenclature may include (a) Full Analysis Set (FAS) (b) Total Sebelipase Alfa
- Subpopulation(s) or special population(s) descriptions will provide sufficient detail to ensure comprehension of the population (eg, ITT Females, PP Males greater than 60 years of age) used for analysis in a table or figure.
- Population sizes may be presented as the total in the column header as (N=xx) where appropriate.
- Population sizes shown with summary statistics are the sample sizes (n) of patients with non-missing values.
- All population summaries for categorical variables will include all categories that were planned and for which the patients may have had a response. If no subject is counted in a category, the count of 0 will be displayed. Percentages corresponding to null categories (cells) will be suppressed.
- All percentages are rounded to the nearest percent and reported without decimal points (xx %). A percentage of 100% will be reported as 100%. If an output displays both count and percent contiguously (e.g. "5 (50%)" where n=10), and the count is 0, then "0%" will not be displayed, only the count of "0" will be displayed. If the count is not presented, only the percentage, then "0%" will be displayed.
- Population summaries that include p-values will report the p-value to 3 decimal places with a leading zero (0.001). All p-values reported on default output from statistical software may be reported at the default level of precision; p-values less than 0.001 will be reported as "<0.001," not "0.000."

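### Read literally, the percentage denominator counts infants with no growth assessment as not underweight, stunted or wasted, so these secondary percentages can only be understated

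*Protocol*

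**What the plan says.** Protocol Section 8.1 gives a general rule with no exception: "When percentages are reported, the number of treated subjects will be used as the denominator". The same section presents efficacy tables for the PES, so for those tables the treated subjects are the treated infants in that set. SAP 7.1 sets a similar but softer default: the "denominator for the percentage calculation will be based upon the total number of subjects in the study population for the group, unless otherwise specified".

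Protocol Section 8.7 says that "the percentages of subjects who meet criteria for underweight, stunting, and wasting will be tabulated for each timepoint". SAP 9.1 repeats this and adds the cut-offs (below -2 SD). Neither names a denominator. SAP 2.2.2 lists the three indicators as secondary efficacy endpoints.

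On missing values, SAP 7.1.1 states: "Missing data will not be imputed". For the primary endpoint only, Protocol Section 8.7 classifies an infant with unknown status: "a subject who is not confirmed to have survived to 12 months of age will not be considered to have met the primary endpoint". Growth status has no such rule.

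SAP 12.1 says that the n shown with summary statistics is the non-missing count, and illustrates a count with its percentage as 5 (50%) for an n of 10. SAP 13, which lists changes from the protocol's analyses, mentions only the Denver II total score.

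**The concern.** An all-treated denominator is conservative for a good outcome. In the survival endpoint an unconfirmed infant counts as a failure, and the result can only look worse. Underweight, stunting and wasting are bad outcomes, so the same denominator works the other way: an infant with no measurement is in effect shown as free of the condition.

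Absence is unlikely to be unrelated to growth. Protocol Section 3.2.2.1 describes growth failure as a main contributor to death in this disease. The displayed share of affected infants could therefore fall from visit to visit because infants have died, and a reader could take that for improvement. With about 8 infants in the set, one absence visibly moves a percentage.

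**Working it through.** **The plan's own figures.** The documents give no figure for growth-status percentages. The nearest is the planning scenario in Protocol Section 8.2: 8 infants in the PES, 6 surviving to 12 months. The exact Clopper-Pearson limits are the 2.5% quantile of Beta(x, n-x+1) and the 97.5% quantile of Beta(x+1, n-x). For 6/8 they are (34.91%, 96.81%), and for the natural history group, 1/18, they are (0.14%, 27.29%). Both match the protocol. The scenario supplies the 8 treated and 6 alive used below.

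**Formula.** Let N be treated PES infants, m those assessed at the visit, and x those assessed who meet the criterion.

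- Observed percentage: x/m
- Displayed under the literal rule: x/N = (x/m) × (m/N)

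Whenever m < N and x > 0, the displayed value is the lower one. The two agree if everyone is assessed or nobody assessed is affected.

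**N = 8, m = 6 (factor 6/8 = 0.75).** The values of x are assumptions and cover every non-zero count.

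| x | Observed x/6 | Displayed x/8 | Gap (points) |
|---|---|---|---|
| 1 | 16.7% | 12.5% | 4.2 |
| 2 | 33.3% | 25.0% | 8.3 |
| 3 | 50.0% | 37.5% | 12.5 |
| 4 | 66.7% | 50.0% | 16.7 |
| 5 | 83.3% | 62.5% | 20.8 |
| 6 | 100% | 75.0% | 25.0 |

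SAP 12.1 requires whole percentages ("All percentages are rounded to the nearest percent and reported without decimal points"), so 37.5% prints as 38%.

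**N = 8, m = 7 (factor 7/8 = 0.875).** The gap runs from 1/7 - 1/8 = 14.3% - 12.5% = 1.8 points to 7/7 - 7/8 = 12.5 points.

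**Two examples in which no child's growth status changes (counts assumed).**

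- *One affected and one unaffected infant die.* Baseline is 4/8 = 50%. Afterwards the observed share is 3/6 = 50% and the displayed share is 3/8 = 37.5%, an apparent fall of 12.5 points.
- *Two affected infants die.* Baseline is 6/8 = 75%. Afterwards the observed share is 4/6 = 66.7% and the displayed share is 4/8 = 50%. The displayed fall is 25 points. The observed share also falls, by 8.3 points, because the deaths were selective.

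**Counting the two deaths as meeting the criterion.** The first example gives (3 + 2)/8 = 62.5%, the second (4 + 2)/8 = 75%. This is an upper bound, not an estimate: in the first example it exceeds the baseline share.

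**The case against.** The best counter-argument is that the SAP may intend observed cases. SAP 12.1 defines the displayed n as non-missing, and its worked percentage divides by n. SAP 7.1 speaks only in general terms and allows exceptions. Refusing imputation also fits an observed-case denominator at least as well as one that silently classes absent infants as unaffected. Protocol Section 8.1 defers analytical detail to the SAP, and SAP 15 puts the table layouts in an addendum that is not among these documents.

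This stands to the extent that the SAP is ambiguous and the final tables might use assessed infants. It does not settle the matter. SAP 12.1 gives a display convention and an example, not a rule for percentages; SAP 12 says that changes to that appendix are not SAP amendments; and SAP 13 declares no departure from the protocol's denominator. The protocol sentence remains unqualified.

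It is also fair to say that the losses can be seen elsewhere. Continuous summaries report the non-missing n (SAP 7.1), so the z-score tables show how many infants were assessed. Disposition counts and Kaplan-Meier curves show who has left.

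Finally, an observed-case denominator is no complete cure, as the second example shows: survivors are a selected group. That limits the simple fix and is a reason to add a sensitivity row, not a reason to keep the literal rule.

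**Conclusion.** The point holds as a minor one. Taken literally, the protocol's denominator understates the by-timepoint underweight, stunting and wasting percentages whenever a PES infant is unassessed and at least one assessed infant is affected. With 8 treated and 6 assessed the shortfall is 4 to 25 points; with 7 assessed it is about 2 to 12.5. The numbers affected are assumed throughout. The planning scenario concerns survival to 12 months of age, whereas the growth tables run on time since first infusion, so the full gap would appear only at visits after both losses.

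Three stronger readings go beyond the documents.

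- A reader might infer that the final tables will certainly be biased. The SAP wording is too open for that, and the table layouts are not available here.
- A reader might infer that the efficacy conclusion is compromised. The primary endpoint counts unconfirmed infants as failures, the z-score summaries do not use this denominator, and Protocol Section 8.11.1 plans no formal tests.
- A reader might add infants who have not reached later visits when the 12-month report is cut. Protocol Section 12 can be read as cutting each infant's data at 12 months of age. But Section 8 places all planned secondary analyses at that point, and these include survival at 18 and 24 months, so the size of any such effect cannot be fixed from the text.

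**What to change.** In Protocol Section 8.1 and SAP 7.1 and 9.1, state that by-timepoint underweight, stunting and wasting percentages use PES infants with a non-missing assessment at that timepoint. Show each as n/N, with the numbers dead, withdrawn, missed and not yet due beside it.

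Because survivors are selected, add one sensitivity row that counts PES infants who died or withdrew as meeting the criterion, labelled as an upper bound. The two rows together show how far the result depends on who is left.

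The cost is about one sentence in each place, matching wording in the table layouts, and trivial programming. The drawback is that later-visit percentages will rest on small numbers and look less favourable than under the literal rule.

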1.4 Clinical Data

The clinical development program is investigating the safety and tolerability of sebelipase alfa and its clinically meaningful effects on the medical complications of LAL Deficiency. LAL-CL01, a Phase 1/2 dose-finding study in adults with LAL Deficiency, has completed. An extension study, LAL-CL04, is ongoing in subjects who completed LAL-CL01. LAL-CL03 is an ongoing Phase 2/3 study to evaluate the safety, tolerability, efficacy, PK and pharmacodynamics (PD) of sebelipase alfa in pediatric subjects with LAL Deficiency who developed growth failure or other clinical evidence of rapidly progressive LAL Deficiency before 6 months of age. LAL-CL02 is an ongoing Phase 3 study to evaluate efficacy, safety, and PK of sebelipase alfa or placebo in pediatric and adult subjects with LAL Deficiency who may not have been eligible for other studies. LAL-CL08 is a Phase 2 study in infant subjects with rapidly progressive LAL Deficiency. Please refer to the IB for further information on the clinical experience with sebelipase alfa.

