1.5 Dose Rationale and Risk/Benefits

1.5.1 Dose Rationale

In this study, sebelipase alfa will be administered at a starting dose of 0.35 mg/kg qw and all subjects will receive a dose increase to 1 mg/kg (contingent on safety), with an option for a further dose increase to 3 mg/kg qw. These doses of sebelipase alfa were selected based on the following:

- As discussed in Section 1.4, clinical data are available from a completed study in patients with LAL Deficiency (LAL-CL01) administered qw infusions of sebelipase alfa at doses of 0.35 mg/kg, 1 mg/kg, or 3 mg/kg as well as 1 mg/kg, or 3 mg/kg qow (LAL-CL04). These data show:
 - All 3 dose levels of sebelipase alfa were well tolerated.
 - Sebelipase alfa therapy produced rapid and comparable reductions in serum transaminases at all 3 dose levels.
 - Increases in serum lipids were seen at all 3 dose levels within 4 weeks of treatment initiation, consistent with the known mechanism of action of sebelipase alfa. These effects were more marked with the 3 mg/kg qw dose and may therefore be dose related. Compared to a dose of 3 mg/kg qw, doses of 0.35 and 1 mg/kg qw may have less marked short-term effects on serum lipids, but a potentially comparable clinical benefit.

- Maintenance of clinical response (reduction in ALT and AST and improvement of lipid levels) was observed in adult subjects treated with qow dosing in LAL-CL04.
- There is an adequate safety margin for sebelipase alfa based on nonclinical toxicology studies. Refer to the IB for further information.
 - There were no meaningful toxicological findings in 4-week repeated dose toxicology studies in the Sprague-Dawley rat and Cynomolgus monkey at doses up to 50 mg/kg. Based on the human equivalent doses in rats (8.1 mg/kg) and monkeys (16.1 mg/kg), this represents an approximately 23.0- to 46.1-fold safety margin relative to the planned starting dose of 0.35 mg/kg in the current study.
 - Sebelipase alfa was well tolerated in a 6-month repeated dose toxicity study in Cynomolgus monkeys given qw IV infusions at doses up to 30 mg/kg. Based on the human equivalent dose (9.7 mg/kg), this provides an approximately 27.7-fold safety margin relative to the planned starting dose of 0.35 mg/kg in the current study. The absence of any sebelipase alfa related changes in study parameters supports the long-term dosing with sebelipase alfa.

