- Alkaline phosphatase, gamma glutamyltransferase (GGT), albumin, and direct (conjugated), indirect (unconjugated), and total bilirubin levels;
- Liver and spleen size/volume, as measured by ultrasound or magnetic resonance imaging (MRI);
- Hepatomegaly and/or splenomegaly (abdominal girth, liver size, and spleen size) by physical examination;
- Platelet levels;
- Serum lipid levels (total cholesterol, triglycerides, high density lipoprotein [HDL], and LDL).

Because LAL Deficiency presenting in infancy is rapidly progressive and patients often die within 6 months of age (Assmann, 2001, *The Metabolic and Molecular Basis of Inherited Disease*), information on development is limited in this patient population. The potential extended life expectancy in subjects receiving long-term treatment with sebelipase alfa provides an opportunity to improve the medical community's understanding of the developmental process in infants with LAL Deficiency treated with sebelipase alfa. To this end, the study will include an exploratory analysis of developmental outcomes, as assessed by the Denver II developmental screening test.

Dietary changes, including discontinuation of a low-fat/low-cholesterol diet and/or introduction of an unrestricted age-appropriate diet, will also be evaluated on an exploratory basis.

Given the potential for ADAs to alter the PD effect of sebelipase alfa, the impact of ADAs on efficacy endpoints will be explored.

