5.1.11 Laboratory Assessments

Blood and urine samples for laboratory tests will be collected at the timepoints specified in Appendix A.

Prior to any dose change, serum lipid, serum liver, hematology, chemistry, ferritin and hs-CRP shall be obtained. Serum lipid and serum liver assessments should be taken 4, 8, and 12 weeks following any study drug or lipid drug dose change.

Due to the limitations on the volume of blood collection that is considered to be acceptable in young children with very small total circulating blood volumes (see Section 5), the laboratory samples will be ranked in the order corresponding to the study objectives, as shown in Table 2. Only Tier 1 assessments are considered mandatory and all efforts should be made to collect these in all subjects. Samples for the Tier 2 and Tier 3 assessments will only be collected if the blood volume threshold for subject's weight, as well as the subject's clinical status, permit (see Section 5 for further details).

Tier 1 (Mandatory)	
CBC/Hematology:	White blood cell count, red blood cell count, hemoglobin, hematocrit, MCV, MCH, MCHC, platelet count, neutrophil, lymphocytes, monocytes, eosinophils, basophils, peripheral smear for examination of cell morphology
Chemistry Panel:	Glucose, urea nitrogen, creatinine, sodium, potassium, chloride, calcium, magnesium, inorganic phosphorus, total protein, lactate dehydrogenase
Liver Function Tests:	AST/SGOT, ALT/SGPT, alkaline phosphatase, GGT, albumin, bilirubin (direct, indirect, total)
Anti-drug Antibody:	Anti- sebelipase alfa antibody
Urinalysis:	pH, glucose, ketones, blood, protein, nitrite, and leukocytes (microscopic examination will only be done if blood, nitrite and/or leukocytes are abnormal)

Table 2Clinical Laboratory Tests, By Tier

Page 40 of 76

Coagulation Studies:	PT (INR), aPTT					
DNA Sample	See Section 5.1.15					
LAL Enzyme Activity	See Section 5.1.16					
Tier 2 (Optional)						
Lipid Panel:	Total cholesterol, triglyceride, HDL, LDL					
Other Chemistry:	Serum ferritin					
Tier 3 (Optional)						
Pharmacokinetic Assessments	See Section 5.1.14					
Exploratory Biomarkers	See Section 5.1.13					

Coagulation studies are required at Screening only. Thereafter, they should be completed only if the preceding assessment was abnormal or if it is clinically indicated based on emerging evidence of liver dysfunction.

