2.2.3 Exploratory Endpoints

Exploratory efficacy endpoints are:

- changes and/or percent changes from baseline (or first available measurement if baseline data are unavailable) in
 - o alkaline phosphatase, gamma glutamyltransferase (GGT), albumin, and direct (conjugated), indirect (unconjugated), and total bilirubin levels;
 - o liver and spleen size/volume, as measured by ultrasound or magnetic resonance imaging (MRI);
 - hepatomegaly and/or splenomegaly (abdominal girth, liver size, and spleen size) by physical examination;
 - o platelet levels;

- o serum lipid levels (total cholesterol, triglycerides, high density lipoprotein (HDL), low density lipoprotein (LDL).
- Dietary changes, including discontinuation of a low-fat/low-cholesterol diet and/or introduction of an unrestricted age-appropriate diet.
- Denver II developmental screening test: four functional area scores (fine motor-adaptive, gross motor, personal-social, and language skills).
- The impact of anti-SBC-102 antibodies (ADAs) on efficacy endpoints will also be explored.

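### For serum lipids, an on-treatment substitute baseline could distort change scores, because the protocol itself expects lipids to rise soon after treatment starts

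*Protocol*

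**What the plan says.** Protocol 8.1 gives the general rule: "Baseline will be defined as the last measurement prior to the first infusion of sebelipase alfa". It then makes an exception for exploratory analyses, under which "the first available measurement after initiation of treatment may be used as baseline if a pretreatment measurement is unavailable".

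Protocol 3.2.2.1 repeats the exception for the exploratory efficacy parameters, and serum lipids (total cholesterol, triglycerides, HDL and LDL) are in that list. SAP 2.2.3 carries it over as "changes and/or percent changes from baseline (or first available measurement if baseline data are unavailable) in" a list that again includes the four lipids. SAP 9.1 plans tables of observed values, changes and percent changes for them.

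On the expected course, Protocol 1.5.1 states: "Increases in serum lipids were seen at all 3 dose levels within 4 weeks of treatment initiation". It links this to the mechanism of action. Section 1.1.3 describes early lipid mobilization and then correction of dyslipidemia as dosing continues.

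On sampling, Table 2 in Protocol 5.1.11 places the lipid panel ("Total cholesterol, triglyceride, HDL, LDL") in Tier 2, which is drawn only if blood volume and clinical status allow.

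Neither document exempts lipids from the substitution, limits how late the substitute may be taken, or asks for substituted values to be flagged or for results without them.

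**The concern.** A baseline taken after the first infusion is harmless only if the marker has not yet moved. For lipids the protocol expects early movement, in the direction opposite to the later one. A substitute drawn during an early rise is too high a reference, and every later value is then judged against it.

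The exploratory objective in Protocol 2.3 is to determine the drug's effects on lipid parameters. Three things could go wrong in the change tables:

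- A later fall in total cholesterol, LDL or triglycerides would look larger than it was.
- A later increase in HDL would look smaller than it was, or even like a fall.
- The early rise, itself a treatment effect, would not appear for that child.

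With so few subjects, a handful of substituted baselines can move a group mean visibly.

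**Working it through.** The plan gives no figure for this point, so there is none to reproduce. The check concerns the direction of the bias and its size over an assumed range.

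**Inputs from the documents**

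- Direction of the early change: upward, within 4 weeks, at all three dose levels (Protocol 1.5.1). Size not given.
- Direction of the later change: correction of dyslipidemia (Protocol 1.1.3). Size not given.
- Subjects in the efficacy tables: about 8 in the Primary Efficacy Analysis Set (Protocol 8.1 and 8.2), out of about 10 enrolled (Protocol 4.2).
- Likely timing of the first on-treatment lipid sample: Protocol 3.1.1.2 and 5.1.11 call for serum lipids before any dose change, and Protocol 3.1 plans an increase for every subject after 2 weekly infusions if safety allows. A sample is therefore due at about Week 2, inside the 4-week window.

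**Assumed inputs**

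- r, the proportional rise at the substitute sample: 20%, 30% or 50%.
- L, the later value divided by the true pre-treatment value.

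**Formulas**

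- True change = L - 1.
- Apparent change from the substitute = L/(1 + r) - 1.
- For any r > 0 the second is lower than the first.

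**Per-child results**

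| Case | r = 20% | r = 30% | r = 50% |
|---|---|---|---|
| Back to pre-treatment level (L = 1.0, true change 0%) | 1/1.2 - 1 = -16.7% | 1/1.3 - 1 = -23.1% | 1/1.5 - 1 = -33.3% |
| True 20% fall (L = 0.8) | 0.8/1.2 - 1 = -33.3% | 0.8/1.3 - 1 = -38.5% | 0.8/1.5 - 1 = -46.7% |
| True 10% increase, as might be hoped for HDL (L = 1.1) | 1.1/1.2 - 1 = -8.3% | 1.1/1.3 - 1 = -15.4% | 1.1/1.5 - 1 = -26.7% |

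**Group mean**, 8 subjects, no true change in any of them:

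- One substituted baseline: -16.7/8 = -2.1 points at r = 20%, and -33.3/8 = -4.2 points at r = 50%.
- Three substituted baselines: three times as much, about -6.3 to -12.5 points.

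**Opposite case.** If the first sample comes late, when the level is already at 90% of the true baseline, a true 20% fall reads as 0.8/0.9 - 1 = -11.1%. The effect is then understated.

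**Is a missing pre-dose value plausible?** The schedule in Appendix A offers clinical laboratory tests at Screening and again before the Week 0 dose, so there are two chances. Against that, lipids are optional and rank below the Tier 1 tests. DNA, LAL activity and coagulation are Tier 1 tests due at Screening, and Protocol 5 limits a single draw to 1% of blood volume. SAP 3 also notes one subject who began treatment under compassionate use. The documents do not say whether that child has a pre-treatment lipid value, and they give no expected frequency of missing values.

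**The case against.** The strongest reply is that the bias is conditional and its reach is narrow.

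- The early rise is not documented in this population. It was reported from "LAL-CL01, a Phase 1/2 dose-finding study in adults with LAL Deficiency", and Protocol 1.1.1 describes a different clinical picture in infants. Protocol 1.5.1 adds that "doses of 0.35 and 1 mg/kg qw may have less marked short-term effects on serum lipids", and those are the doses of the first weeks here. This stands: r is unknown and could be small.
- The rule is permissive, confined to exploratory analyses, and used only where no pre-treatment value exists. This also stands.
- The reporting gives some protection. All data are listed, observed values are tabulated beside changes, SAP 10.2 plans individual plots of actual values for all four lipids, and Protocol 8.11.1 plans no formal tests. A careful reader of about 10 trajectories could see a missing pre-dose point. This limits the harm, but the change tables would still carry the distorted figures unmarked.
- SAP Section 2 describes itself as orienting text copied from the protocol, SAP 9.1 refers only to baseline, and SAP 7.1.1 rules out imputation. Whether the substitution is operative in the SAP is therefore unclear, which is itself a reason to settle it.

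A reader might infer that any first post-dose lipid value must be a drug-induced high, or that the lipid objective would be answered wrongly in the drug's favour. The documents do not support either. They neither show nor quantify a rise in infants, the direction reverses for a late first sample, and for HDL the bias runs against the drug if an increase is the benefit. Nor does either document claim that the substitution is conservative.

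**Conclusion.** The point holds in a limited form. The documents permit an on-treatment baseline for a group of markers that the protocol itself reports as rising early. They also make a missing pre-dose value foreseeable, and their sampling rules make an early substitute the more likely case. If the substitute falls within a rise, the direction of the error is certain. Its size is not: the false change of 17% to 33% for a child with no true change rests on an assumed rise of 20% to 50%, and the shift of 2 to 4 points per substituted child rests in addition on a table of 8 subjects. The primary survival endpoint and the secondary endpoints are untouched. This is an inexpensive improvement to an exploratory, descriptive analysis and not a threat to the trial's main conclusions.

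**What to change.** State in the SAP that summaries of lipid change and percent change include only subjects with a pre-dose value. List and plot the observed lipid values of the other subjects without a change score. If substituted baselines are shown at all, flag them, give the time of the substitute sample, and present results with and without them. Align Protocol 3.2.2.1 and 8.1 at the next amendment. That step needs IRB/IEC approval under Protocol 11, so it is not worth a separate amendment.

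The cost is a sentence or two in the SAP, at most one extra display, and fewer of the roughly 8 to 10 subjects in the lipid change tables. In a study this small that loss is noticeable, but the listings and plots keep the excluded children visible.
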